5. STUDY ASSESSMENTS AND PROCEDURES

5.1. Study Flow Chart

A detailed study flow chart (with all assessments) is displayed hereafter.

Clinical Study Protocol

Study code: ABX464-004

	Screening	Days				Treatment interruption - Follow-up					
Time Window	± 7 days	± 2 days (except D25 ± 4)			± 2 days						
Days	D-21	D0	D7	D14	D21	D25	D28	Twice weekly for 3 weeks	Every week till VR	ARTs reintroduction visit	FU visit(s)***
Obtained Inform Consent	x										
Check of IN/EX Criteria	x	x									
Physical Examination	x	X	X	X	Х	X	Х		Х	X	Х
Body Weight (kg)	X	X	X	X	Х	X	Х		х	x	Х
Height Measurement (cm)	x										
Medical History	X			[
Medical Calls to patients		Day	3&5								
Serology: HBV, HCV, HIV	x										
Hematology + Biochemistry	x	x	х	x	х	x	х		х	x	X****
CD4 and CD8 count	X	х	Х	X	Х	X	Х	X	Х	X	Х
Urinalysis	X	X	Х	X	Х	X	х		X	x	
Blood Pregnancy test	X			l				1			
Urine pregnancy test	X	X	Х	X	X	X	х		X	X	
Vital signs	X	X	Х	X	Х	X	Х	1	Х	x	
ECG (12 lead)	X	Х	Х				Х			х	
DRV/RTV-COBI prescription	x	x	х	x	х	x	х			х	х
ABX464/placebo treatment dispensation and patient diary review		x	x	x	x	x	x				
Blood samples drug pK		х*	Х*	X*	Х*	X**					
Blood samples for viral load /miRNA	x	x	x	x	x	х	x	x	х	x	х
Genotyping										Х	
Leukopheresis (optional)	x									x	
Blood samples for reservoir assessment • Viral DNA		x					х			x	
TILDA Adverse Events	X	x	x	x	x	x			x	x	х
recording * pre DRV/RTV or DRV/C	DBI marning doce	^	^		^	^	^		^	^	

** pre DRV/RTV or DRV/COBI morning dose, 0.5, 1, 1.5, 2, 2.5, 3, 3.5, 4, 6, 8, 12 and 24 h post-dose (hospitalization is not required)

*** Every 14 days till undetectable VL

**** only bioschemistry required and for at least 28 days after treatment interruption

5.2. Study conduct

It is the investigator's responsibility to ensure that all the assessments are carried out during each visit and that the intervals between visits/follow-ups are adhered to.

5.2.1. Screening Visit (21 ± 7 days prior to baseline)

The patient will be informed about the general aspects of the study and will sign the screening informed consent form. The patient number will be allocated once the patient will be created in the eCRF. Only when consent has been given may further study procedures be carried out. During the screening phase, the following assessments will be performed:

- Signed informed consent form;
- Demographic data: date of birth and gender;

- Medical history, including Peak Viral Load and Nadir from patient's medical file (if available);
- Physical examination and vital signs;
- Hematology;
- Biochemistry and urinalysis including pregnancy test for all women of childbearing potential;
- Serology (HIV, HBV, HCV) Previous HIV serology results are accepted;
- Viral Load, CD4/CD8 count;
- Blood collection for HIV reservoir assessment;
- 12 leads ECG;
- Leukopheresis (Optional);
- Record all medications received within 3 months prior to baseline and note if the medication is continuing;
- Inclusion/exclusion criteria will be verified globally.

5.2.2. Randomization Visit / Day 0 - Baseline

- Physical examination and vital signs;
- Hematology;
- Biochemistry and urinalysis;
- 12 leads ECG;
- Viral Load, CD4/CD8 count;
- Urine pregnancy test for all women of childbearing potential;
- Adverse Events reporting;
- Perform Pk blood sample (pre DRV/RTV or COBI morning dose);
- Blood collection for HIV reservoir assessment;
- Only patients who meet all of the inclusion and randomization criteria and none of the exclusion criteria will be randomized;
- Complete e-CRF to register patient;
- Adverse event assessment;
- Dispense study treatment (allocated by SODIA) to patient and instruct how to take them.

5.2.3. D7, D14, D21 Visits (± 2 days)

- Physical examination and vital signs;
- Medical calls to patient (on Day 3 and Day 5);
- Hematology;
- Biochemistry and urinalysis;
- Viral Load, CD4/CD8 count;
- 12 leads ECG (only at Day 7);
- Perform Pk blood sample (pre DRV/RTV or COBI morning dose);
- Urine pregnancy test for all women of childbearing potential;
- Adverse Events reporting;
- Dispense study treatment at each study visit to patient and instruct how to take them.

5.2.4. D25 Visit (± 4 days)

• Physical examination and vital signs;

- Perform Pk blood samples (pre DRV/RTV or COBI morning dose, 0.5, 1, 1.5, 2, 2.5, 3, 3.5, 4, 6, 8, 12, and 24 h post-dose);
- Adverse Events reporting.

Of note, according to the time-window allowed, this visit could be performed on Day 21 or Day 28 if needed.

5.2.5. Day 28 Visit (± 2 days)

- Physical examination and vital signs;
- Hematology;
- Biochemistry and urinalysis;
- Viral Load, CD4/CD8 count;
- Urine pregnancy test for all women of childbearing potential;
- 12 leads ECG,
- Blood collection for HIV reservoir assessment;
- Check treatment compliance;
- Adverse Events reporting;
- Stop all treatments (DRV/RTV or COBI + ABX464/placebo);
- Schedule next patient visits.

5.2.6. Treatment interruption period Visits (\pm 2 days)

During the treatment interruption period study visits should be performed weekly until viral load rebounds. The following examination should be performed during these visits.

- Physical examination and vital signs;
- Hematology;
- Biochemistry and urinalysis;
- Viral Load, CD4/CD8 count;
- Blood collection for HIV reservoir assessment;
- Urine pregnancy test for all women of childbearing potential;
- Adverse Events reporting.

However, during the first three weeks (after treatment interruption), the Viral Load and the CD4/CD8 count should be controlled twice a week.

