2.2. Secondary Objectives

The secondary objectives are:

- To evaluate the long-lasting effect of ABX464 on the viral load after treatment stop (i.e. Day 29) using the Time to Viral Rebound versus placebo;
- To compare the effect of ABX464 on viral load (HIV RNA) versus placebo from Day 0 to Viral Rebound;
- To compare the effect of ABX464 on the CD4+ T cell counts versus placebo from Day 0 to Viral Rebound;
- To compare the effect of ABX464 on the CD4+/CD8+ T cells ratio versus placebo from Day 0 to Viral Rebound;
- To evaluate the effect of ABX464 on HIV reservoir (pro-viral DNA in PBMC) versus from Day 0 to Viral Rebound.
- To assess the Pharmacokinetics parameters of ABX464 given on top of darunavir/ritonavir/cobicistat and ABX464.
- To compare miRNA modulations and tropism of HIV versus placebo from Day 0 to Viral Rebound.

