5.2.7. Viral Rebound – ART reintroduction Visit

This visit should be performed in all patients who experienced a viral rebound or who have been prematurely discontinued from the study (before the treatment interruption phase- End of Study visit).

Following examinations/procedures should be performed:

- Physical examination and vital signs;
- Hematology;
- Biochemistry and urinalysis;
- Viral Load, CD4/CD8 count;
- 12 lead ECG;
- Leukopheresis (Optional);
- Urine pregnancy test for all women of childbearing potential;

- Blood collection for HIV reservoir assessment;
- Adverse Events reporting;
- HIV genotyping (if ARTs have been stopped);
- Resume ARTs (if applicable).

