5.3.5. Viral load and HIV Reservoirs assessment

Regarding HIV viral load, local laboratories will be used as this is done in routine for HIV infected patients and as method is standardized so that comparisons between laboratories can be performed.

The total HIV-DNA level quantified in blood cells is an indirect marker of HIV reservoir. It is predictive of disease progression, to progression to CD4+ T cells count lower than 300 cells per mm³ and to death.

Total and integrated HIV-DNA will be quantified at Day -21, Day 0 and then at the pre-specified visits (cf. flowchart).

30 ml of blood for Viral DNA assays and 60ml for the TILDA assays will be withdrawn at the pre-specified visits (cf. flowchart). PBMC will be prepared and frozen at study site according a study specific procedure. Frozen PBMC will be sent to the Department of Internal Medicine and Infectious Diseases Ghent University and Ghent University Hospital [name], Belgium.

Total HIV DNA will be quantified using HIV DNA assay. This assay is based on real time PCR technology with the amplification of the LTR gene. To differentiate total cell-associated HIV-DNA from integrated HIV-DNA levels, different mode of DNA extraction will be used on identical aliquots of frozen PBMC (previously separated by Ficoll-Hypaque). Both markers will be quantified within the same technique and the same standard of quantification. Results will be expressed as the number of HIV-DNA copies/millions of PBMC; using the blood formula and CD4+ T cells count, the frequency per million of CD4+ T cells will be estimated.

Clinical Study Protocol

In addition, depending on the number of PBMC collected using a stepwise approach the following assays could be performed: integrated DNA, Full length CA RNA, Spliced CA RNA, 2LTR circles, Tilda, VOA and the integration sites of the HIV.

Sub and optional study on the reservoir: molecular identity of the earliest rebounding virus and the T cells that harbor this virus.

Should ABX464 delay rebound in some but not all treated patients we will be able to examine how the source of rebound virus has been altered by the treatment in order to guide the design of future studies.

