5.4. Summary of blood samples

The Table 2 below summarizes the volume of blood to be sampled at each study visit.

Summary of Maximal Blood Volume (mL)	
Day - 21	26 mL + 60 ml (TILDA)
Day O	23 mL + 30 ml (reservoirs)
Day 7	24 mL
Day 14	24 mL
Day 21	24 mL
Day 25	52 mL
Day 28	24 mL + 30 ml (reservoirs)
TOTAL	317 mL
Follow-up (every week) - Reservoir and genotyping at Viral Rebound only	20 ml + 90 ml (TILDA and reservoirs) + 2 ml genotyping
Follow-up visit post ARTs reintroduction	15 mL

Laboratory testing	Tube	Volume (ml)
Glucose	Fluoride (2 cc)	2
Biochemistry	Heparin blood (6 cc)	6
Hematology	EDTA (3 cc)	3
H8V, HCV, HIV screen	Clotted blood (6 cc)	6
HIV RNA	EDTA (6 cc)	6
HIV Reservoir / TILDA	EDTA tube (7 cc) for PBMC collection	30 / 60
CD4 and CD8	EDTA (3 cc)	3
PK (per time point)	Heparin blood (4 cc)	4

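### Section 5.2.6 orders reservoir blood at every weekly interruption visit, but Table 2 and the flow chart restrict it to rebound; following 5.2.6 takes at least 50 mL where the stated maximum is 20 mL

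*Protocol*

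**What the plan says.** Four parts of the protocol bear on reservoir blood after Day 28.

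- **Section 5.2.6** covers the weekly visits until viral load rebounds. It states "The following examination should be performed during these visits", and the list that follows includes "Blood collection for HIV reservoir assessment". No volume is given, and nothing limits the draw to rebound.
- **Section 5.4, Table 2** presents its figures as maximal volumes. The weekly follow-up row gives 20 mL, plus 90 mL (TILDA and reservoirs) and 2 mL (genotyping), with the restriction "Reservoir and genotyping at Viral Rebound only".
- **Section 5.1, flow chart.** The viral DNA row under "Blood samples for reservoir assessment" is marked at D0, D28 and the ART reintroduction visit. It is blank in both interruption columns (twice weekly for 3 weeks, and every week until rebound).
- **Section 5.2.7**, the ART reintroduction visit, lists reservoir blood again: "This visit should be performed in all patients who experienced a viral rebound".

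Section 5.3.5 sets 30 mL for viral DNA and 60 mL for TILDA and refers to the flow chart for the timing. Section 5.2 makes the investigator responsible for seeing that every assessment is done at each visit.

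**The concern.** Section 5.2.6 is the text a site works from when it runs an interruption visit. Read as written, it calls for a reservoir draw every week. Table 2 and the flow chart call for none until rebound. Following 5.2.6 breaches the protocol's own volume maximum; following Table 2 omits a listed examination.

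Two things are at stake. The first is unplanned blood. The excess grows with time to rebound, so the patients with the longest control give the most. The second is uneven data for the secondary reservoir objective in section 2.2, which runs from Day 0 to Viral Rebound. Sites that follow the chart return three viral DNA time points per patient, and sites that follow 5.2.6 add one per week. With 28 to 36 patients at up to 8 sites, the sampling pattern would then depend on which page a site used.

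**Working it through.** **1. Reproduce Table 2.** Screening to Day 28: (26+60) + (23+30) + 24 + 24 + 24 + 52 + (24+30) = 317 mL, as stated.

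**2. What the weekly 20 mL contains.** From the tube table in 5.4: glucose 2 + biochemistry 6 + hematology 3 + HIV RNA 6 + CD4/CD8 3 = 20 mL. This accounts for the full figure, so it contains no reservoir tube. At rebound the figure is 20 + 90 + 2 = 112 mL, where 90 = 30 (viral DNA) + 60 (TILDA).

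**3. Volume implied by the line in 5.2.6.** Reservoir blood is listed in the same terms at Day 0 (5.2.2) and Day 28 (5.2.5), where Table 2 assigns 30 mL. That is the lowest volume the protocol gives it. A weekly visit then takes 20 + 30 = 50 mL, and 50/20 = 2.5 times the maximum.

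**4. Excess at the planning medians** (section 9.4: 7 days on placebo, 28 days on ABX464). Weekly draws number 0 versus 3 if the visit that detects rebound is not counted, and 1 versus 4 if it is. The difference is 3 draws either way, 3 × 30 = 90 mL. With exponential times to rebound (an assumption), mean weekly draws are 1.0 versus 4.6–4.7 before rebound, or 2.0 versus 5.5–5.6 with the detecting visit. The difference is 3.5–3.7 draws, about 105–112 mL.

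**5. No rebound by 3 months** (section 3.2; 12–13 weekly visits assumed). With k weekly visits, the schedule in the flow chart and Table 2 takes 20k + 9 × min(k, 3) mL. The 9 mL is viral load 6 + CD4/CD8 3 at the second visit in each of the first three weeks. Following 5.2.6 adds 30k.

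| k | Interruption, chart | Total from screening, chart | Added by 5.2.6 | Total from screening, 5.2.6 |
|---|---|---|---|---|
| 12 | 240 + 27 = 267 mL | 317 + 267 = 584 mL | 360 mL | 944 mL |
| 13 | 260 + 27 = 287 mL | 317 + 287 = 604 mL | 390 mL | 994 mL |

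All totals are before the ART reintroduction visit. If TILDA were also drawn weekly, which no section schedules, the excess would be 90 mL per visit.

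**The case against.** The strongest reply is that the protocol resolves this itself. Section 5.3.5 refers the draws to the flow chart, and the chart and Table 2 agree, so one line in 5.2.6 is the outlier. This is right about what was probably intended, and it supports correcting 5.2.6. It does not stop a site working from the visit list from drawing the blood.

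A second reply is that the line means the rebound draw, since Table 2 puts the 90 mL in its weekly row, conditional on rebound. That may explain how the line arose. But 5.2.6 leaves out the condition, and 5.2.7 already orders the sample.

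Third, the volume is not fixed. Reservoir blood means 60 mL of TILDA at screening and 90 mL at rebound. This stands, and 30 mL is used here only as a lower bound.

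Fourth, the totals near one litre are a tail case. Under exponential times with a 28-day median, the proportion without rebound at 12–13 weeks is 2^-3 to 2^-3.25, roughly 10–12% or 2–3 of 21 ABX464 patients, and almost no placebo patients. This stands too. The 90 mL at the 28-day median is the more typical figure.

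Finally, every patient who rebounds gives viral DNA at D0, D28 and rebound under either reading, so the common time points are intact and no bias is shown. That is correct. The point is uneven sampling between sites, and whether sites would in fact divide is not known.

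**Conclusion.** The contradiction holds. Section 5.2.6, if followed, takes at least 50 mL at each weekly visit against a stated maximum of 20 mL. The excess is 90 mL at the 28-day median and 360–390 mL for a patient without rebound over 3 months. The figures rest on 30 mL per draw, weekly attendance as scheduled, and 12–13 weekly visits in 3 months. The TILDA line of the flow chart cannot be read reliably apart from the adverse-event row in the copy available, so nothing here depends on it.

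The consequences are modest. The extra draws fall after all treatment has stopped. They do not touch power, the time-to-rebound analysis or on-treatment safety data. The text should still be corrected, because it instructs sites to exceed the protocol's own limit.

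**What to change.** Delete the reservoir line from the list in 5.2.6, or qualify it as *at viral rebound only (see 5.2.7)*. Table 2, the flow chart and 5.2.7 can then stand as written.

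The cost is one edited line. The only thing given up is weekly reservoir data between Day 28 and rebound, which Table 2 and the flow chart do not provide for anyway.

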5.2.7. Viral Rebound – ART reintroduction Visit

This visit should be performed in all patients who experienced a viral rebound or who have been prematurely discontinued from the study (before the treatment interruption phase- End of Study visit).

Following examinations/procedures should be performed:

- Physical examination and vital signs;
- Hematology;
- Biochemistry and urinalysis;
- Viral Load, CD4/CD8 count;
- 12 lead ECG;
- Leukopheresis (Optional);
- Urine pregnancy test for all women of childbearing potential;

- Blood collection for HIV reservoir assessment;
- Adverse Events reporting;
- HIV genotyping (if ARTs have been stopped);
- Resume ARTs (if applicable).

5.2.8. Follow-up Visits – HIV control restauration (\pm 2 days)

For patients who have stopped ARTs (DRV/RTV or COBI + ABX464/placebo) and have experienced a viral rebound, some follow-up visits, every 14 days, after ARTs reintroduction will be performed until the viral load has returned to undetectable levels. The last follow up will be considered the End of Study visit.

Following examinations/procedures should be performed:

- Physical examination and vital signs;
- Biochemistry;
- Viral Load, CD4/CD8 count;
- Adverse Events reporting;

5.3. Detail of the study assessments

5.3.1. Physical Examination and Vital Signs

A routine physical examination (including body weight) will be done at each study visit. Physical examinations will cover eyes, ears, nose, throat, lungs/thorax, heart/cardiovascular system, abdomen, skin and mucosae, nervous system, lymph nodes, musculo-skeletal system, and, if applicable, others. Any new clinically relevant finding compared to baseline must be documented as adverse event.

Measurements of vital signs will be done at each visit (Blood pressure, Heart Rate, Body temperature). The patient should rest for at least 15 minutes prior to measurements. The measurements can be performed either in sitting or supine position of the patient. The right or left arm may be used. However, the position and the arm used for measurement should be kept constant throughout the trial for an individual patient.

The investigator should ensure that each parameter outside the normal range is assessed for clinical significance. For any deviation assessed clinically significant, the investigator has to document the change as an AE in the CRF.

In addition, it is at the discretion of the investigator to document any change or trend over time in vital signs as an AE if he considers the change to be clinically significant, even if the absolute value is within the alert limit or reference range.

5.3.2. Pregnancy

For all female patients of childbearing potential, a blood pregnancy test (beta human chorionic gonadotropin [HCG]) will be performed at Day 0. In addition, a urine pregnancy test will be performed at each of the study visit until Viral Rebound.

In case of positive pregnancy testing, detailed procedures can be found in section 8.3.2.

5.3.3. ECG

Electrocardiograms have to be done at Screening, Day 0, Day 7, Day 28 and ART reintroduction visit and, if clinically indicated, at follow-up. At least a 12-lead ECG with recordings of at least 6 action potentials in lead II (paper speed 25mm/s, amplitude 10mm/mV) has to be done in a resting position. Prior to the recording the patient should be at rest for at least five minutes. Resting ECG should be performed before any examinations.

The ECG printout will be reviewed by the investigator and a signed and dated copy of the ECG will be attached to the medical file. The original ECG printouts are considered as source data and should be stored at site. In case thermal paper is used, a copy of the original ECG must be kept as well. All abnormal findings must be

documented in the CRF. Any clinically relevant findings compared to Visit V0 must be documented as adverse events.

5.3.4. Hematology and biochemistry

For hematology and biochemistry local laboratories will be used. All laboratory results and reference ranges for safety parameters must be entered in the eCRF. Each laboratory value that is outside of the institution's normal range will be identified. The investigator will be responsible for assessing the clinical significance of laboratory abnormalities. If the investigator is uncertain about the clinical significance of a laboratory abnormality, he/she will consult with the Sponsor medical monitor. The investigator should follow any clinically significant laboratory abnormalities until resolution.

Table 1 displays the clinical laboratory parameters that must be measured.

Table 1: Laboratory Tests

HEMATOLOGY	BIOCHEMISTRY
Hemoglobin	Sodium
Hematocrit	Potassium
WBC	Chloride
Neutrophils	Calcium
Lymphocytes	Phosphate
Monocytes	Glucose
Eosinophils	BUN or urea
Basophils	Creatinine
Platelet count	AST
	ALT
	GLDH
	Alkaline phosphatase
	gGT
	Total bilirubín
	Total protein
	Albumin
	LDH
	CRP

At each biochemistry timepoint, a tube containing the remaining sera (at least 1 mL) should be kept and stored at -20°C for potential further liver function parameters such as soluble caspase-cleaved keratin 18 (M30 Elisa) and/or miRNA22 as a marker of early hepatotoxicity.

5.3.5. Viral load and HIV Reservoirs assessment

Regarding HIV viral load, local laboratories will be used as this is done in routine for HIV infected patients and as method is standardized so that comparisons between laboratories can be performed.

The total HIV-DNA level quantified in blood cells is an indirect marker of HIV reservoir. It is predictive of disease progression, to progression to CD4+ T cells count lower than 300 cells per mm³ and to death.

Total and integrated HIV-DNA will be quantified at Day -21, Day 0 and then at the pre-specified visits (cf. flowchart).

30 ml of blood for Viral DNA assays and 60ml for the TILDA assays will be withdrawn at the pre-specified visits (cf. flowchart). PBMC will be prepared and frozen at study site according a study specific procedure. Frozen PBMC will be sent to the Department of Internal Medicine and Infectious Diseases Ghent University and Ghent University Hospital [name], Belgium.

Total HIV DNA will be quantified using HIV DNA assay. This assay is based on real time PCR technology with the amplification of the LTR gene. To differentiate total cell-associated HIV-DNA from integrated HIV-DNA levels, different mode of DNA extraction will be used on identical aliquots of frozen PBMC (previously separated by Ficoll-Hypaque). Both markers will be quantified within the same technique and the same standard of quantification. Results will be expressed as the number of HIV-DNA copies/millions of PBMC; using the blood formula and CD4+ T cells count, the frequency per million of CD4+ T cells will be estimated.

Clinical Study Protocol

In addition, depending on the number of PBMC collected using a stepwise approach the following assays could be performed: integrated DNA, Full length CA RNA, Spliced CA RNA, 2LTR circles, Tilda, VOA and the integration sites of the HIV.

Sub and optional study on the reservoir: molecular identity of the earliest rebounding virus and the T cells that harbor this virus.

Should ABX464 delay rebound in some but not all treated patients we will be able to examine how the source of rebound virus has been altered by the treatment in order to guide the design of future studies.

Given the possibility that the ABX 464 treatment arm will rebound over a more prolonged period, we will be able to study the T cells that are the source of the early or late rebound and compare them to T cells that rebound in the control arm. This data may help identify the characteristics of a latently infected T cell that ABX 464 is most likely to maintain in a prolonged quiescent state.

Specific Aims:

- 1. Determine the sequence of the rebounding founder virus.
- 2. Determine the T cell receptor and viral integration site of the T cells harboring the rebounding virus.

We will use an assay to detect HIV infected cells in order to pair the sequence of the rebounding virus with a specific T cell clonotype containing matching integrated pro-viral DNA. We will accomplish this by pairing high sensitivity sequencing of plasma viremia and sorting of latently infected T cells. This assay to determine the HIV integration site, genome wide HIV proviral sequence and TCR alpha/beta sequence at a single cell level has been developed at the Institute for Immunology and Infectious Diseases, Perth, Australia, directed by [name].

In order to optimally carry out these studies, we will require leukopheresis specimens to obtain at least 5 billion PBMC. We will anticipate sorting 200 latently infected cells per subject. This will assure that we capture not only CD4+ T cells that are only making transcript, but also the replication competent virus that is contributing to rebound. Assuming a conservative estimate of one HIV infected cell per million CD4+ T cells, we would need to process 200 million CD4+ T cells.

The leukopheresis prior to the initiation of the study (screening visit), will enable us to catalogue the identity (based on TCR sequence and integration site) of latently infected T cells prior to study drug and treatment interruption. The second leukopheresis at or shortly after rebound (ART reintroduction visit) will allow discrimination of newly infected cells associated with viremia and other infected cells coming out of the reservoir. This opt-in ancillary study will be performed after receiving informed consent of the patients.

5.3.6. miRNA modulation

ABX464 up-regulates miRNA in non-infected and infected PBMCs, making of this micro-RNA a potentially useful biomarker for ABX464 treatment monitoring. The miRNA assays will be performed from the remaining plasma collected for viral load determination. No specific blood sample are therefore needed. Determination of miRNA level in plasma will be performed in order to assess treatment effect by comparing before and after treatment. Assays for miRNA determination and tropism test will be conducted by Theradiag, [name], France.

Blood collected in EDTA tubes should be store at room temperature (20-22°C) and processed within 4 hours after collection. Plasma isolation consist in a centrifugation at 500 G during 10 min at room temperature followed by the storage of 900 μ L de plasma in an eppendorf tube at -80°C (or -20°C) until the end of the study. The plasma should be collected from all viral load samples.

